6.1 Registration

- ◆ Histologically confirmed de novo (primary) glioblastoma before or at the time of first progression after RT concurrent/adjuvant TMZ chemotherapy
 - In case of testing at the time of first progression: either at least 3 months after the end of radiotherapy or have tumor progression that is clearly outside the radiation field or have tumor progression unequivocally proven by surgery/biopsy
- ◆ Confirmation that biological material (at least from initial diagnosis and if further resection had been performed at recurrence) to determine diagnosis is available for central review
- Written informed consent for central EGFR screening must be given according to ICH/GCP, and national/local regulations

6.2 Before randomization

All pretreatment evaluations should be performed within 2 weeks before randomization.

The baseline evaluations include:

- Histologically confirmed *de novo* (primary) glioblastoma with unequivocal first progression after RT concurrent/adjuvant TMZ chemotherapy either at least 3 months after the end of radiotherapy or have tumor progression that is clearly outside the radiation field or have tumor progression unequivocally proven by surgery/biopsy
- Informed consent and consent for future studies
- Demographics (height, weight, race, ethnicity)
- Complete medical history, including documentation of any clinically significant medical condition
- Prior anti-cancer therapy (including start and end dates for prior TMZ chemotherapy and RT)
- Physical examination including, but not limited to, WHO performance status and neurological evaluation
- Ocular examination by an ophthalmologist
- Vital signs (blood pressure, pulse rate and body temperature)
- Quality of life assessment, including EORTC QLQ-C30 and EORTC-BN20 (see section [10.1](#))
- 12-lead ECG
- ◆ Concomitant medications
- ◆ Steroid intake
- Assessment of all adverse events according to CTCAE 4.0
- Hematology (WBC, absolute neutrophil count, lymphocytes, hematocrit, hemoglobin and platelet count)
- Biochemistry (serum creatinine, total bilirubin, ASAT, ALAT, alkaline phosphatase, phosphate, total protein, albumin, sodium, potassium, calcium and chloride)
- Serum or urine pregnancy test for WOCBP within 72 hours prior to randomization.
- Gadolinium-enhanced MRI of the brain within 2 weeks prior to randomization. For operated patients, the post-surgery MRI within 48 hours is mandatory and can be used as baseline. However, if a subject is not randomized within 2 weeks from the post-surgery MRI, then a new MRI scan is required and will be used as baseline.
- Demonstrated EGFR gene amplification by centralized testing using EGFR FISH developed by Abbott Molecular.
- Although not considered necessary activities prior to randomization, the following samples are optional and all subjects randomized may consent to participate in future translational research:
 - Tumor tissue remaining following EGFR amplification testing for future TR projects (optional samples, see section [11.8](#))
 - Whole blood for germline DNA and TR projects (optional samples, see section [11.8](#))

6.3 From treatment start until end of protocol treatment

6.3.1 Day 1 of each cycle

All day 1 evaluations should be performed and laboratory results reviewed within 3 days before or at day 1 of the cycle, and prior to dosing. For day 1 of cycle 1, if the evaluations listed below have been already performed during the screening phase and within 2 weeks prior to this day 1, the same results can be used for cycle 1 and tests do not need to be repeated.

- Physical examination including, but not limited to, WHO performance status and neurological evaluation
- Ocular examination if clinically indicated (Arms 1 and 2 only)
- Hematology and biochemistry (as section 6.2)
- Vital signs (as section 6.2)
- Weight
- 12-lead ECG immediately after ABT-414 dosing on day 1 of cycle 1 and cycle 3, for subjects assigned to ABT-414 (Arm 1 or 2)
- Assessment of all adverse events according to CTCAE 4.0
- Concomitant medications, including steroid intake (maximal intake (mg per day)).

For patients in Arm 3A, lomustine, the above physical examination, hematology, vital signs and adverse event assessments need to be repeated at day 28 (+/- 3 days).

6.3.2 Day 1 and day 5 for cycles 1 and 2; day 1 for cycle 3 and every 2 cycles thereafter (day 1 of C5, C7 etc.)

- Pharmacogenetic (PG) sample: optional sample collection for all subjects that consent. If the PG sample is not collected at the Day 1 visit, it may be collected anytime during the study.
- For subjects assigned to ABT-414 (Arm 2) or ABT-414 in combination with TMZ (Arm 1): Pharmacokinetic (PK) and pharmacodynamic (PD) sample collection according to the following schedule. Refer to the study specific laboratory manual for detailed instructions on sample collection, volumes, processing and shipment.

	Cycle 1 Day 1 of ABT-414	Cycle 1 Day 5 (Day 4 up to day 7 is acceptable) of ABT-414	Cycle 2 Day 1 of ABT-414	Cycle 2 Day 5 (Day 4 up to day 7 is acceptable) of ABT-414	Cycle 3 Day 1 of ABT-414	Cycle 5, Cycle 7 etc. Every two cycles starting from ABT- 414 cycle 5	35 Day Safety Follow- up
PK – ABT-414, and Total ABT- 806 Assays	X ^a	X ^e	X ^a	X ^e	X ^a	X ^b	X ^c
PK - Cys- mcMMAF assay	X ^a	X ^e	X ^a	X ^e	X ^a	X ^b	
PK Antidrug Antibody Assay (ADA/nADA)	X ^b		X ^b		X ^b	X ^b	X ^c
PD Plasma Markers	X ^b		X ^b		X ^b		
PD serum markers	X ^b		X ^b		X ^b		
PG Sample (Optional)	X ^d						

- a. Samples will be collected before infusion (0 hour, pre-dose) and immediately after ABT-414 infusion
- b. Samples will be collected before infusion (0 hour, pre-dose).
- c. Samples will be collected 35 days (within a two-day window) after last ABT-414 infusion for subjects able to return to the clinic for the follow-up visit.
- d. If the pharmacogenetic sample is not collect at this visit, it may be collected anytime during the study.
- e. Samples will be collected 96 hrs post ABT-414 infusion, but may be collected from 4 up to 7 days post infusion.

The date/time of collection of each PK/ADA/PD/PG sample will be recorded. The date, start and end time of each ABT-414 infusion will be recorded on the appropriate eCRF.

Dose administration information will be collected for subjects receiving TMZ and lomustine and will be recorded on the appropriate eCRF.

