In the ongoing phase I study, as of April 29 2015, 40 subjects have been treated in Arm B and 42 in Arm C. Common treatment emergent AEs in at least 30% of subjects in Arm B included photophobia (15/37.5%), blurred vision (23/57.5%), nausea (19/47.5%), fatigue (17/42.5%) and headache (12/30%); in Arm C, they were blurred vision (25/59.5%) and fatigue (24/57.1%). Grade 3/4 AEs found in > 10% of subjects in Arm B included keratitis (5/12.5%), gamma GT elevation (4/10%) and decreased platelet (4/10%); in Arm C, the only grade 3/4 AEs of > 10% was keratitis (6/14.3%). Overall, in the 1.25 mg/kg dose cohort the grade 3/4 ocular toxicity rate was 27%. ABT-414 administration was suspended in those who developed grade 3/4 eye toxicity until symptoms recovered to grade 1, which took a median of 40 days.

Because of the high rate of significant eye toxicity and the need for drug interruption, the starting dose of ABT-414 for the present study for both Arm 1 and 2 will be 1.00 mg/kg.

Additional Safety Information:

Preliminary safety data were available for 488 subjects who received at least 1 dose of ABT-414 in 4 open-label studies at the most recent IB update (version 7.0). This Phase 2 Study M14-483 (INTELLANCE-2) in recurrent GBM is the only trial for which safety data from a control arm (TMZ or lomustine monotherapy) is available. Adverse events reported for more than 20% of subjects receiving ABT-414

were fatigue (34.9%), vision blurred (27.3%), headache and keratitis (25.0% for each), dry eye (24.4%) and corneal epithelial microcysts (22.1%). The majority of subjects who received ABT-414 (77.3%) experienced at least 1 Treatment Emergent Adverse Event coded to the Standard Organ Class of Eye Disorders. In addition to ocular side effects related to corneal epitheliopathy, treatment-emergent adverse events reported by $\geq 10\%$ of subjects in the ABT-414 treatment groups and $\geq 5\%$ more frequently than the lomustine/TMZ control group included headache, fatigue, constipation, and liver transaminase elevations (alanine aminotransferase and aspartate aminotransferase). The rate of constipation was mainly accounted for by the ABT-414/TMZ combination arm, for which the rate was similar to that of subjects receiving TMZ monotherapy.

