6.3.3 Day 14 of each cycle - Arm 1 and 2 patients only

All day 14 evaluations should be performed and laboratory results reviewed within 3 days before or at day of dosing of ABT-414.

- Physical examination including, but not limited to, WHO performance status and neurological evaluation
- Ocular examination if clinically indicated
- Vital signs (as section 6.2)
- Hematology (as section 6.2)
- Assessment of all adverse events according to CTCAE 4.

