6.5 Summary table

	Before registration	Registration	Baseline 2 wks prior to randomization	Randomization				During protocol treatment, each cycle				Every 8 weeks	EoT ⁹	6 months after randomization	Follow-up			
				Day 1 ⁰	Day 14 Arm 1 & 2	Day 21 Arm 1 and 3B	Day 28 Arm 3A ¹⁴	Day 1 ⁰	Day 14 Arm 1 & 2	Day 21 Arm 1 and 3B	Day 28 Arm 3A ¹⁴				every 12 weeks			
PIS/IC for registration (EGFR)	X																	
Histology	X		X															
WHO Performance Status			X															X
Biological samples for central EGFR assessment	X																	
EGFR gene amplification			X															
Biological samples for TR projects (optional)			X															
PIS/IC for study			X															
Weight			X															
Medical his. & Demographic			X															
Whole blood for germline DNA and TR projects (optional)			X															
Prior anti-cancer therapies			X															
Physical examination ¹			X															X
Vital signs			X															X ¹⁰

	Before registration	Registration	Baseline 2 wks prior to randomization	Randomization	During protocol treatment, each cycle				Every 8 weeks	EoT ⁹	6 months after randomization	Follow-up every 12 weeks
					Day 1 ⁰	Day 14 Arm 1 & 2	Day 21 Arm 1 and 3B	Day 28 Arm 3A ¹⁴				
Quality of life assessment			X					X ⁸		X		
ECG			X									
Concomitant medication collection			X						X		X ¹⁰	
Steroid intake			X						X		X	
Prophylactic eye drops ¹⁵						X						
Adverse events (CTCAE v.4.0)			X						X		X ¹¹	
Hematology ²			X			X ⁷						
Biochemistry ³			X									
Serum/urine pregnancy test			X ⁴									
Plk samples									X ⁹			
PD samples												
PG samples (optional)												
Gd-MRI			X					X				
Survival and further anti-cancer treatments											X	

0 For day 1 of cycle 1, if the evaluations listed here have been already performed during the screening phase and within 2 weeks prior to this day 1, the same results can be used for cycle 1 and tests do not need to be repeated: physical examination including, but not limited to, WHO performance status and neurological evaluation; ocular examination if clinically indicated; hematology and biochemistry; vital signs; weight.

- 1 Physical examination including neurological evaluation, and ocular examination at baseline and if clinically indicated
- 2 Including WBC, absolute neutrophil count, lymphocytes, hematocrit, hemoglobin and platelet count

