11.2.1 Adverse Events of Special Interest (AESI)

The number and percentage of subjects having AESI will be tabulated by MedDRA system organ class and preferred term. Specific AESI will be identified by the following search criteria in [Table 7](#).

Table 7. Adverse Events of Special Interest

Adverse Event of Special Interest	Search Criteria	Event Definition/ Medical Concept
Microcystic Keratopathy	CMQ "80000152"; Preferred Terms: Acquired corneal dystrophy, Ciliary hyperaemia, Corneal abrasion, Corneal cyst, Corneal decompensation, Corneal defect, Corneal degeneration, Corneal deposits, Corneal disorder, Corneal dystrophy, Corneal epithelial microcysts, Corneal epithelium defect, Corneal erosion, Corneal irritation, Corneal lesion, Corneal oedema, Corneal opacity, Deposit eye, Dry eye, Eye pain, Foreign body sensation in eyes, Keratitis, Keratopathy, Lacrimation increased, Limbal swelling, Ocular toxicity, Photophobia, Slit-lamp tests abnormal, Topography corneal abnormal, Vision blurred	Any adverse event report identified by search criterion

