11.2.1.2 Time to Onset of Adverse Event of Special Interest

For specified AESIs, time to the first occurrence (onset) the event will be assessed using survival analysis methodology (Kaplan-Meier estimates) separately for all AESIs, for all AESIs with NCI CTCAE grade ≥ 2 , and for all AESIs with NCI CTCAE grade ≥ 3 .

Time to onset will be measured in days relative to the day of a subject's first dose of study drug (ABT-414/TMZ/lomustine) to the start date of the first occurrence of AESI. If a subject has not experienced an AESI, the subject will be censored on the day of the subject's last assessment (i.e., the day of the subject's last known laboratory assessment, last known vital sign assessment, last known physical exam, last known ocular exam, last known tumor assessment, or last known follow-up visit, whichever is the latest) or 35 days from the subject's last ABT-414 treatment, whichever is earliest; if the subject has not experienced an AESI and had no post-baseline assessment (i.e., none of laboratory assessment, vital sign assessment, physical exam, ocular exam, or tumor assessment), the subject will be censored on the day of the subject's first study drug (ABT-414/TMZ/lomustine).

Median onset time will be estimated using a Kaplan-Meier method with corresponding 95% CI for the median for each treatment arm.

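### On-treatment eye examination is scheduled only for Arms 1 and 2, so ocular AESI results that pool corneal findings with symptoms are not fully comparable with control, and the protocol contradicts itself on who may be examined

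*Protocol*

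**What the plan says.** **Who is examined**
- Before randomization every patient has an "Ocular examination by an ophthalmologist" (protocol 6.2).
- On Day 1 of each cycle, protocol 6.3.1 lists "Ocular examination if clinically indicated (Arms 1 and 2 only". Section 6.3.3, headed "Day 14 of each cycle - Arm 1 and 2 patients only", lists a further eye examination, again only when indicated.
- The other on-treatment and end-of-treatment visits (6.3.4 to 6.3.8) list no eye examination.
- Protocol 5.5.1.3, which concerns ABT-414 toxicity, makes an ophthalmologist's slit-lamp examination compulsory once ocular toxicity appears and calls for repeat examinations at grades 1 and 2. The lomustine and TMZ sections (5.5.2, 5.5.3) have no counterpart.
- Footnote 1 of the summary table (6.5) reads "Physical examination including neurological evaluation, and ocular examination at baseline and if clinically indicated". Footnote 0 also names the eye examination. Neither mentions an arm, and SAP Table 1 repeats both.
- The 12-weekly follow-up after treatment (6.4) lists an eye examination when indicated, for all arms.

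**What is reported**
- SAP Table 7 (11.2.1) defines one ocular AESI from a single list of preferred terms. Corneal findings such as "Corneal epithelial microcysts, Corneal epithelium defect, Corneal erosion" stand beside symptoms such as photophobia.
- SAP 11.2 puts any AESI in the overview table by arm and overall. SAP 11.2.1 adds a table by preferred term, and 11.2.1.1 adds counts by grade.
- SAP 11.2.1.2 plans time to onset for all AESIs, for grade ≥2 and for grade ≥3: "Median onset time will be estimated using a Kaplan-Meier method with corresponding 95% CI for the median for each treatment arm".

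**The concern.** A finding that needs an eye examination is recorded only if someone looks. If the schedule prompts that look in two arms and not in the third, part of any difference in corneal findings reflects who was examined rather than what the drug did. The AESI definition does not separate the terms that depend on examination from those that do not, and the SAP does not mention the unequal scheduling.

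The contrast with control will be read even without a formal test. Protocol 1.7 describes this as the only ABT-414 trial with control-arm safety data, and it already picks out events by how much more frequent they are than under lomustine or TMZ. The trial is open label, so sites know which schedule applies to each patient.

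**Working it through.** **1. The examination passages side by side.** Section 6.3.1 names Arms 1 and 2, and 6.3.3 is a visit for those arms only. Footnotes 0 and 1 permit an indicated examination with no arm named. Both cannot describe the same schedule.

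**2. Does the unrestricted follow-up examination close the gap?** Section 6.4 sets visits every 12 weeks ± 14 days after the last dose. The first falls at 84 − 14 = 70 to 84 + 14 = 98 days. The SAP's treatment-emergent window closes 35 days after the last dose (SAP 11.1), and routine adverse event collection closes at 49 days (protocol 7.2.1.8). The first follow-up visit is later than both, so the gap stays open.

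**3. What the AESI contains.** Table 7 lists 30 preferred terms. Six are plainly symptoms: vision blurred, photophobia, eye pain, dry eye, lacrimation increased, and foreign body sensation. Most of the other 24 are corneal findings or diagnoses. This split is a reading of the list, since the SAP makes none.

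**4. Which outputs are exposed.** Examination in Arms 1 and 2 is itself prompted by clinical indication.
- A patient who is examined will usually already have a symptom term from the list. That patient counts under any AESI and has a first onset date without the examination. A control patient with the same symptom counts in the same way.
- The arms part afterwards. In Arms 1 and 2, protocol 5.5.1.3 requires a slit-lamp examination and repeats, which can add a corneal term, possibly at a higher grade. In Arm 3 nothing in the schedule prompts this.
- The exposed outputs are therefore mainly the pooled higher-grade AESI counts, the grade ≥2 and ≥3 onset curves, and the rows for individual corneal terms.

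**5. The plan's own figures for severe events.** Protocol 1.7 gives phase I grade 3/4 keratitis as 5/40 = 12.5% (Arm B, with TMZ) and 6/42 = 14.3% (Arm C, monotherapy). Both reproduce. It is the most frequent grade 3/4 event listed in each arm; for the second, "in Arm C, the only grade 3/4 AEs of > 10% was keratitis (6/14.3%)". Keratitis is a Table 7 term. These rates come from treated patients and say nothing about how many findings would be missed in control.

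**6. Illustration; every rate is assumed.** Let p be the true rate of an examination-only finding, equal in both arms, with all ABT-414 cases examined and a fraction e of control cases examined. The artificial difference is p × (1 − e). With 240/3 = 80 patients per arm:

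| p | e = 0 | e = 0.25 | e = 0.5 | e = 1 |
|---|---|---|---|---|
| 2% | 2 points (1.6 patients) | 1.5 (1.2) | 1 (0.8) | 0 |
| 5% | 5 points (4.0 patients) | 3.75 (3.0) | 2.5 (2.0) | 0 |
| 10% | 10 points (8.0 patients) | 7.5 (6.0) | 5 (4.0) | 0 |

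**The case against.** The case against is substantial, and most of it stands as a limit on the point.

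- **Nothing forbids examining a control patient.** A reader might infer from 6.3.1 that Arm 3 cannot register corneal findings at all. The documents do not support that. Section 6.3.1 lists visit procedures and prohibits nothing, the footnotes allow an indicated examination, and protocol 7.2.1 records adverse events in every arm however they come to light.
- **The headline outputs are largely protected.** Because symptoms trigger the examination, pooling symptoms with findings makes the any-AESI count and its first onset less dependent on examination. This stands, and it confines the concern to the outputs in step 4.
- **No formal comparison is planned.** SAP 11.1 rules out between-arm tests and p-values for safety, and the preferred-term table lets a reader separate the terms. Both are correct. But that table does not show how many patients were examined, so a near-empty corneal row in Arm 3 could mean no disease or no examination. The grade-restricted onset curves remain pooled.
- **SAP 11.2.1.1 names no arms**, and three of its seven items concern ABT-414 only. This weakens the point for that section. It does not affect the overview table or 11.2.1.2, which cover the arms expressly.
- **A share of AESI reports cannot be derived.** A reader might add the rates in protocol 1.7 (vision blurred 27.3%, keratitis 25.0%, dry eye 24.4%, corneal epithelial microcysts 22.1%) and conclude that 47.1/98.8, about 48%, of AESI reports depend on examination. That is not valid. The four rates sum to 98.8 points while only 77.3% of patients had any eye disorder event, so patients are counted more than once. The list is also cut off at terms above 20%.

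**Conclusion.** The point holds as a minor one. Two things are established from the text: the passages on eye examination contradict each other, and the visit schedule makes examination-based corneal findings less likely to be recorded in Arm 3 within the treatment-emergent window. The consequence is limited to the higher-grade AESI results, the grade ≥2 and ≥3 onset curves, and the individual corneal-term rows.

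The documents give no figure for the size of the distortion. The table in the working shows only how it scales. It applies to an examination-only term and depends on assumed rates and examination fractions; at equal examination it vanishes.

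A reader might go further and conclude that the leading grade 3/4 event, keratitis, is invisible in control. That would require keratitis to be recorded only on examination, which is an assumption the documents do not make.

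**What to change.** **SAP 11.2.1 to 11.2.1.2.** Split Table 7 into a symptom group and an examination-based group, with the classification of each term fixed in the SAP. Report both on the safety population, including the counts by grade and the onset curves. Read any contrast with Arm 3 from the symptom group. State that on-treatment eye examination was scheduled unequally.

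Give the number of patients examined on treatment in each arm as context only. It should not serve as a denominator, because patients are examined for symptoms and a rate among them would be inflated by selection. SAP 11.2.1.2 already uses the date of the last ocular examination for censoring, so examination dates should be available.

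**Protocol.** Reconcile 6.3.1 and 6.3.3 with footnotes 0 and 1 of the summary table, and carry the result into SAP Table 1. Which examination rule should apply is for the study team.

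**While editing 11.2.1.2.** Its censoring rule counts 35 days from the last ABT-414 treatment, a date that does not exist for Arm 3, although results are planned for each arm.

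**Cost.** SAP wording and one table split. The downside is two AESI rows instead of one, and a judgement on how to classify terms such as keratitis.

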6.3.3 Day 14 of each cycle - Arm 1 and 2 patients only

All day 14 evaluations should be performed and laboratory results reviewed within 3 days before or at day of dosing of ABT-414.

- Physical examination including, but not limited to, WHO performance status and neurological evaluation
- Ocular examination if clinically indicated
- Vital signs (as section 6.2)
- Hematology (as section 6.2)
- Assessment of all adverse events according to CTCAE 4.

6.3.4 Day 21 of each cycle - Arm 1 and 3B patients only

All day 21 evaluations should be performed within 3 days before or 3 days after day 21 of the cycle.

- Hematology (as 6.2 - this can be omitted once treatment at the present dose level was shown to cause only grade 1 or less hematological toxicity at day 21 and only grade 2 or less at day 28).

